11.5.5.1 Analysis of endpoint

The proportion of infants with increase in WAZ ≥ 0.3 , 0.4, and 0.5 at Day 56 with 95% CIs will be estimated and presented in a table by treatment group. The binomial mid-P method will be used to estimate the CIs.

Log-binomial regression will be used to estimate the risk ratio of rates of increase in WAZ > 0.3, 0.4 and 0.5 at Day 56 between Bi-26 and Placebo, adjusting for the following covariates: baseline WAZ, age (in days), country and discharge destination. The adjusted risk ratio (exponentiated coefficient) with 95% CI will also be presented in the same summary table as the proportion estimates. If the overall rate is less than 15% of all participants or the log-binomial model does not converge, then logistic regression will be used in the place of log-binomial regression and odds ratios will be reported instead of risk ratios, which will be a reasonable estimate of the risk ratios. Separate models will be fitted for each of the outcomes of increase in WAZ > 0.3, 0.4 and 0.5. PROC GLIMMIX will be used for this analysis.

The Safety and PP populations will be used for this analysis.

Increases will be indicated as flags in the WAZ listing described in Section 11.5.2.1.

Confidential Page 35 of 50

11.5.6 Secondary outcome: Proportion of infants with WAZ > -2 at Day 56

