7.1.3 Justification of Sample Size

[figure not shown]
The primary study hypothesis is that the difference in the mean change from baseline in WAZ is larger for participants randomized to at least 28 days of Bi-26 relative to placebo.

For the sample size calculation for the primary hypothesis, it is assumed that the between group difference in the WAZ change from baseline in 0.45 with a standard deviation of 1.3. Based on the above assumption(s) using a 2-sided alpha of 5% and a power of at least 90%, a total of 354 participants, 177 in each group are required.

Confidential Page 14 of 50

Assuming a 10% loss to follow-up and a 3% mortality rate, a sufficient number of participants will be screened to ensure approximately 396 randomly assigned participants are enrolled, 198 in each treatment group.

Figure 2. Sample size sensitivity

N/group, 1-sided $\alpha = 2.5\%$, Power=90%

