Log-binomial regression will be used to estimate the risk ratio of re-hospitalization rates at Day 56 between Bi-26 and Placebo, adjusting for covariates baseline WAZ, age (in days), country and discharge destination. The adjusted risk ratio (exponentiated coefficient) with 95% CI will also be presented in the same summary table. If the overall re-hospitalization rate is less than 15% of all participants or the log-binomial model does not converge, then logistic regression will be used in the place of log-binomial regression. Odds ratios will be reported instead of risk ratios, which will be a reasonable estimate of the risk ratios.

PROC GLIMMIX will be used for this analysis.

Confidential Page 36 of 50

Re-hospitalizations for acute non-surgical illness will be listed in a separate listing for all participants, including date/time of admission, associated SAE, preferred term of SAE and date/time of discharge if discharged.

The Safety and PP populations will be used for this analysis.

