Appendix 3. Summary of Efficacy Analyses

Table 8. Analyses of Efficacy Parameters

Parameter	Population	Statistical Method	Missing Data	Interpretation
CFB in WAZ	mITT	MMRM	Observed cases	Primary analysis
CFB in WAZ	PP	MMRM	Observed cases	Sensitivity
CFB in WAZ	mITT, PP	MMRM adjusted for study intervention compliance	Observed cases	Secondary/Sensitivity
CFB in WAZ	mITT	MMRM with adjustment of confounding variables	Observed Cases	Secondary, Sensitivity
CFB in WAZ adjusted for gestational age	mITT	MMRM	Observed Cases	Sensitivity
CFB in Weight	mITT	MMRM	Observed cases	Key Secondary
Proportion of participants with increase in WAZ \geq 0.3, 0.4, 0.5 at Day 56	Safety, PP	Estimation of proportions with mid-P CIs and logbinomial regression to estimate risk ratio	Observed cases	Secondary, Sensitivity
Proportion of participants with WAZ > - 2	Safety, PP	Estimation of proportions with mid-P CIs and log-binomial regression to estimate risk ratio	Observed cases	Secondary, Sensitivity
Proportion of participants that were rehospitalized	Safety, PP	Neg-binomial model to estimate incidence rate ratio	Observed cases	Secondary, Sensitivity
Proportion of participants that were re-hospitalized	Safety, PP	Estimation of proportions with mid-P CIs and log-binomial model to estimate risk ratio	Observed cases	Secondary, Sensitivity

[figure not shown]
Confidential Page 48 of 50

Proportion of mITT, PP participants that had samples with presence of *B. infantis*

Estimation of proportions with mid-P CIs

Observed cases

[figure not shown]
Secondary, Sensitivity

[figure not shown]

Confidential Page 49 of 50

Page 50 of 50 Confidential

GF0015-MNK01-301 SAP

Gates MRI MNK01-301 SAP Vault eTMF Document Number: VV-TMF-47158 | 1.0

Signature Page for VV-TMF-47158 v1.0

Reason for signing: Approved	Name: Role: Biostatistics Date of signature: 15-Sep-2023 11:21:55 GMT+0000
Reason for signing: Approved	Name: Role: Clinical Development Date of signature: 15-Sep-2023 12:29:06 GMT+0000
Reason for signing: Approved	Name: Role: Biostatistics Date of signature: 15-Sep-2023 13:59:21 GMT+0000

Signature Page for VV-TMF-47158 v1.0

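### When the log-binomial model fails to converge, the SAP swaps the risk ratio for an odds ratio at any event rate and calls it a reasonable estimate, which is untrue for common outcomes with a real effect

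*SAP*

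**What the plan says.** For both responder endpoints the SAP presents the proportion in each arm with a mid-P confidence interval. It adds an adjusted risk ratio from log-binomial regression with baseline WAZ, age, country and discharge destination as covariates. The fallback in 11.5.5.1 begins "If the overall rate is less than 15% of all participants or the log-binomial model does not converge". In either case logistic regression takes over and "odds ratios will be reported instead of risk ratios, which will be a reasonable estimate of the risk ratios". Section 11.5.6.1 repeats the rule for WAZ above -2, and 11.5.7 has it in nearly the same words for re-hospitalization.

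Two further statements matter. In 11.5.5.1, "Separate models will be fitted for each of the outcomes of increase in WAZ" above 0.3, 0.4 and 0.5, and the resulting ratio "will also be presented in the same summary table as the proportion estimates". Appendix 3, Table 8 gives the method for the WAZ-increase endpoints as "Estimation of proportions with mid-P CIs and logbinomial regression to estimate risk ratio". It names the risk ratio for WAZ above -2 and for re-hospitalization too, and lists no alternative measure.

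**The concern.** The two triggers are joined by an *or*, and one justification serves both. An odds ratio is close to a risk ratio when the outcome is rare, so the 15% trigger carries its own support. Non-convergence says nothing about the event rate, and for a common outcome with a real effect the odds ratio lies further from 1 than the risk ratio.

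Two things follow if the branch is entered. The reported ratio would overstate the risk ratio that it is said to approximate. And because each threshold has its own model, one table could hold risk ratios for some thresholds and an odds ratio for another, so that a change of scale reads as a difference between thresholds. The effect measure would then depend on whether an optimiser converged.

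**Working it through.** **Inputs from the documents.** SAP 7.1.3 assumes a "between group difference in the WAZ change from baseline in 0.45 with a standard deviation of 1.3". With a two-sided 5% test and 90% power, the t-test calculation gives 176.3 per group, rounded up to 177. This reproduces the stated 177 per group (354 in total). The documents give no event rate, risk ratio or odds ratio for the binary endpoints.

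**Assumptions not in the documents.** WAZ change is normal with SD 1.3 in both arms, and the placebo mean change m lies between -0.5 and +0.5. For WAZ above -2, baseline is taken as 2/3 uniform on (-3, -2) and 1/3 uniform on (-4, -3), with change independent of baseline. The 2/3 : 1/3 split is the randomization target in SAP 7.2; the shape within each stratum is assumed.

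**Formulas.** With d the true difference and c the threshold:

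- p0 = P(N(m, 1.3) ≥ c) and p1 = P(N(m + d, 1.3) ≥ c). For WAZ above -2, the same probabilities are averaged over the baseline mix.
- RR = p1/p0 and OR = [p1/(1 - p1)] / [p0/(1 - p0)], so OR/RR = (1 - p0)/(1 - p1).

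**Results at the planned d = 0.45.**

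| Endpoint | m | p0 | p1 | RR | OR | OR/RR |
|---|---|---|---|---|---|---|
| Increase ≥ 0.3 | -0.5 | 0.269 | 0.394 | 1.46 | 1.76 | 1.21 |
| Increase ≥ 0.3 | 0 | 0.409 | 0.546 | 1.34 | 1.74 | 1.30 |
| Increase ≥ 0.3 | +0.5 | 0.561 | 0.691 | 1.23 | 1.75 | 1.42 |
| Increase ≥ 0.5 | -0.5 | 0.221 | 0.336 | 1.52 | 1.79 | 1.17 |
| Increase ≥ 0.5 | 0 | 0.350 | 0.485 | 1.38 | 1.74 | 1.26 |
| Increase ≥ 0.5 | +0.5 | 0.500 | 0.635 | 1.27 | 1.74 | 1.37 |
| WAZ > -2 | -0.5 | 0.173 | 0.267 | 1.54 | 1.74 | 1.13 |
| WAZ > -2 | 0 | 0.279 | 0.395 | 1.42 | 1.69 | 1.19 |
| WAZ > -2 | +0.5 | 0.409 | 0.535 | 1.31 | 1.66 | 1.27 |

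The 0.4 threshold falls between the 0.3 and 0.5 rows.

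**OR/RR by true difference, over the same range of m.**

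| d | Increase ≥ 0.3/0.4/0.5 | WAZ > -2 |
|---|---|---|
| 0.45 | 1.17-1.42 | 1.13-1.27 |
| 0.3 | 1.11-1.25 | 1.08-1.17 |
| 0.2 | 1.07-1.16 | 1.05-1.10 |
| 0.1 | 1.03-1.07 | 1.02-1.05 |
| 0 | 1.00 | 1.00 |

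**Which trigger applies.** At d = 0.45 the overall rate is 28-63% for the WAZ increases and 22-47% for WAZ above -2. It drops below 15% only if m is under -1.29, -1.19 or -1.09 (thresholds 0.3, 0.4, 0.5) or under -0.88 (WAZ above -2). Within the assumed range, then, an odds ratio would be reached only through non-convergence. For a WAZ increase at an overall rate of exactly 15%, OR/RR is 1.10 for d = 0.45 (0.110 against 0.190) and 1.04 for d = 0.2 (0.132 against 0.168). The below-15% trigger is therefore acceptable.

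**Mixed scales.** With m = 0 and d = 0.45, suppose only the 0.5 model fails. The table then shows a risk ratio of 1.34 for ≥ 0.3 beside an odds ratio of 1.74 for ≥ 0.5, where the risk ratio is 1.38.

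**Effect of covariate adjustment.** The figures above are marginal, whereas the SAP's ratio is adjusted. A simulation with 354 infants and adjustment for baseline WAZ and age gave OR/RR of 1.18-1.44 for the WAZ increases (thresholds 0.3 and 0.5) and 1.19-1.35 for WAZ above -2. The marginal ranges are, if anything, conservative.

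**How often the model would fail.** This cannot be settled from the documents. In Python simulations, failure for the WAZ increases ran from 0-2% of runs, when the covariates did not predict the change, to most runs when they were assumed to predict it fairly strongly. For WAZ above -2 it was 26-37%, counting fitted probabilities of 1 or more as failures. The covariate strengths are assumptions and PROC GLIMMIX may behave differently. The simulations show that the branch is plausible; no failure rate is claimed.

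**The case against.** The best defence is that the ratio is a supplement. Protocol Table 5 and SAP Table 2 define the population-level summary for these endpoints as frequencies and percentages by arm, and those are reported with confidence intervals whichever model is fitted. The result would be labelled an odds ratio, an adjusted odds ratio from a pre-specified logistic model is a valid measure, its direction is unchanged, and the primary and key secondary analyses are untouched. The largest discrepancies need the full planned effect and a placebo mean that neither document gives. If 1.10 is tolerable under the below-15% trigger, the convergence branch is equally tolerable for WAZ above -2 at a true difference of 0.2 (1.05-1.10) and for both endpoints at 0.1 (at most 1.07). For re-hospitalization no rate is given, and a negative-binomial rate ratio is reported as well.

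All of this stands as a limit on the harm. It does not rescue the sentence: 11.5.5.1, 11.5.6.1 and Table 8 name the risk ratio as what the regression is to estimate, and the claim that the odds ratio stands in for it has no support when the outcome is common. The discrepancy is also largest when the supplement works about as planned, which is when these ratios are most likely to be quoted.

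**Conclusion.** The concern holds and should be fixed. As written, the rule allows an odds ratio to be presented as an approximate risk ratio at any event rate. At the planned effect the odds ratio would be 1.17 to 1.42 times the risk ratio for the WAZ increases and 1.13 to 1.27 times for WAZ above -2. Both ranges rest on a normal change with SD 1.3 and a placebo mean change of -0.5 to +0.5; the second also rests on the assumed baseline distribution. How often the branch would be entered is unknown. With no treatment effect both ratios equal 1, so the switch cannot create an apparent effect. No magnitude is claimed for 11.5.7.

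**What to change.** On non-convergence, keep the risk ratio. Estimate it with the same covariates, either by modified Poisson regression with robust variance or by logistic regression standardised to a risk ratio, and name one of the two in the SAP. In the simulation above the two agreed to about 0.001. Restrict the statement that the odds ratio approximates the risk ratio to the below-15% trigger. Put the same wording in 11.5.5.1, 11.5.6.1 and 11.5.7.

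The cost is SAP wording and a few lines of code, with no new data. Each method has a drawback: modified Poisson can give fitted probabilities above 1 for individual infants, and the standardised estimate needs a delta-method or bootstrap interval.

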| Objectives | Endpoints |
|---------------------------------------------------------------------------------------------------------|---------------------------------------------------------------------------------------------------------------------------|
| Primary | |
| To evaluate the change in weight (standardized for age) of infants receiving Bi-26 | WAZ change from baseline (Day 1) to the Day 56 visit in Bi-26 group |
| Key Secondary | |
| To evaluate the change in weight of infants receiving Bi-26 | Change in weight (in grams) from baseline (Day 1) to the Day 56 visit in the Bi-26 group |
| Other Secondary | |
| To estimate the treatment response over time associated with Bi-26 | WAZ change from baseline (Day 1) over time through the Day 90 visit (longitudinal assessment) by duration of dosing |
| To assess the proportion of infants who achieve a specified change in WAZ from baseline to Day 56 | Proportion of infants with $a \ge 0.3, \ge 0.4$, and ≥ 0.5 change in WAZ from baseline (Day 1) to Day 56 visit |
| To assess the proportion of infants who achieve a specified WAZ at Day 56 | Proportion of infants who achieve a WAZ > -2 at Day 56 visit |
| To assess the re-hospitalization rate | Number of re-hospitalizations for acute non-surgical illness through the Day 56 visit |
| To assess the safety of Bi-26 supplementation through End of Study (EoS, Day 90 visit) | Number of adverse events (AEs) and serious adverse events (SAEs) through Day 90 |
| To measure engraftment of B. infantis in participants | Presence of B. infantis in stool on Days 1, 28, 56, and 90 |

| Objectives | Endpoints |
|------------------------------------------------------------------------------------------------------------------------------|----------------------------------------|
| Exploratory | |
| To describe stool biomarkers in response to Bi-26 supplementation in terms of stool composition (e.g., microbiome, pH) | Stool biomarkers on Days 1, 28, and 56 |
| To describe the blood biomarkers (e.g., inflammation, metabolomics), in response to Bi-26 supplementation | Blood biomarkers on Days 1 and 28 |

Table 2: Schedule of Activities (SoA)

| Activities | | Clinic Visit 1 | | Homo Visits | e 5 | Clinic Visit 2 | Home Visit | Home Visit | Home Visit | Clinic Visit 3 | Clinic Visit 4 | Discon Visit ^b |

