11.5 Efficacy

11.5.1 Calculation of Weight-for-age z-score

WAZ is calculated at Screening and all clinical visits (Days 1, 28, 56, and 90).

The WAZ score is calculated in EDC using the approach defined by the WHO [2]. Given the weight (kg), sex and age (in days) of a participant, the WAZ is calculated as

Confidential Page 31 of 50

$$WAZ = \frac{\left(\left(\frac{Weight}{M}\right)^{L} - 1\right)}{L \times S}$$

where L, M, and S are pre-derived parameter estimates generated by the WHO. L, M, and S are conditional on the Sex and Age (days) of the infant. The lookup tables for the values of L, M, and S can be found on the WHO website [2]. Distinct tables for males and females are given.

WAZ is calculated directly in EDC and need not be derived. WAZ is rounded off to 2 decimals. The value for WAZ (at enrollment) after rounding off is used for randomization and defining the strata $(-3 < \text{WAZ} < -2, \text{WAZ} \le -3)$ (also used for study eligibility).

11.5.2 Primary outcome: CFB in WAZ at Day 56

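### SAP 11.5.5.1 tabulates WAZ gains of at least 0.3, 0.4 and 0.5 but models gains strictly above them, so two responder definitions feed one table

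*SAP*

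**What the plan says.** SAP 11.5.5.1 uses two signs for one endpoint.

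- Proportions: "The proportion of infants with increase in WAZ ≥ 0.3 , 0.4, and 0.5 at Day 56", tabulated by treatment group with mid-P intervals.
- Regression, first mention: the "risk ratio of rates of increase in WAZ > 0.3, 0.4 and 0.5 at Day 56 between Bi-26 and Placebo".
- Regression, second mention: "Separate models will be fitted for each of the outcomes of increase in WAZ > 0.3, 0.4 and 0.5".
- Placement: the adjusted risk ratio "will also be presented in the same summary table as the proportion estimates".

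The regression is log-binomial. Logistic regression replaces it if the overall rate is below 15% or the model does not converge. The same section also flags the increases in the WAZ listing, without saying which sign the flag uses.

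Everywhere else the rule is ≥. Protocol Table 1 ends its list with "and ≥ 0.5 change in WAZ from baseline (Day 1) to Day 56 visit", and SAP 7.3 has the same. Protocol Table 5, SAP Table 2, the SAP 11.5.5 heading and SAP Appendix 3 Table 8 agree. One row of Table 8 covers both the proportions and the regression. SAP section 9, which lists departures from the protocol, mentions no change of threshold.

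On precision, SAP 11.5.1 states: "WAZ is rounded off to 2 decimals". SAP 10.2 defines change from baseline as a plain subtraction and gives no rounding of the difference.

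**The concern.** Because WAZ is kept to 2 decimals, a gain of exactly 0.30, 0.40 or 0.50 is an ordinary value. Such an infant is a responder under ≥ and a non-responder under >. The risk ratio and the proportions beside it could then rest on different counts, and a reader could not reconcile them. Strictly, the risk ratio would also estimate a slightly different endpoint from the one the protocol names, and that change is not declared. Two programmers working from this section could reasonably produce different outputs.

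**Working it through.** **Inputs from the documents (SAP 7.1.3, Protocol 9.4).** Between-group difference in WAZ change 0.45; "with a standard deviation of 1.3"; and "using a 2-sided alpha of 5% and a power of at least 90%, a total of 354 participants, 177 in each group are required".

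**Assumptions not in the documents.** Normally distributed change; placebo mean change 0 to 0.6; an alternative SD of 0.6 to 1.0. The documents give no responder rate for any of the three cut-offs.

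**Step 1. Reproduce the planning figure.** n per group = 2(1.960 + 1.282)² × 1.3² / 0.45² = 175.4, rounded up to 176. The t-test version gives 176.3, rounded up to 177, as stated. Power at 177 per group is 90.3%. The N and SD used below are therefore the plan's own.

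**Step 2. Expected infants exactly on a cut-off c.** For each arm, ties = 177 × [Φ((c + 0.005 − μ)/SD) − Φ((c − 0.005 − μ)/SD)], with the Bi-26 mean 0.45 above placebo. This is about 177 × 0.01 × the normal density at c. Example with SD 1.3, placebo mean 0.3 and c = 0.4:

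- placebo: 177 × 0.00306 = 0.54
- Bi-26: 177 × 0.00296 = 0.52
- total: 1.07 after rounding

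| SD | Ties per cut-off | P(at least one) per cut-off | P(at least one) over three |
|---|---|---|---|
| 1.3 (plan) | 0.99–1.07 | 63–66% | 95–96% |
| 1.0 (assumed) | 1.21–1.38 | 70–75% | 98% |
| 0.8 (assumed) | 1.39–1.70 | 75–82% | 99% |
| 0.6 (assumed) | 1.58–2.19 | 79–89% | more than 99% |

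The probabilities are 1 − exp(−expected ties). For the example, 1 − exp(−1.07) = 66%. Over the three cut-offs at placebo mean 0.3, 1 − exp(−(1.05 + 1.07 + 1.07)) = 96%. These figures apply if the change is held to 2 decimals when the cut is applied.

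**Step 3. If the change is not rounded.** I took every 2-decimal baseline from −6.00 to −2.01 (400 values), added the exact gain, and subtracted in double precision.

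| True gain | Computed below c | Computed equal to c | Computed above c |
|---|---|---|---|
| 0.30 | 265 | 0 | 135 |
| 0.40 | 237 | 0 | 163 |
| 0.50 | 24 | 352 | 24 |

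At 0.3 and 0.4 no computed difference equals the cut-off, so > and ≥ classify every infant alike. But 66% (265/400) and 59% (237/400) of true ties fall on the wrong side of the endpoint definition. At 0.5 the signs differ for 88% of ties (352/400), treating the baselines as equally likely. With 1.05 expected ties at SD 1.3, the chance of a mismatch is 1 − exp(−1.05 × 0.88) = 60%.

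**Step 4. Effect on the crude risk ratio.** I compared the ratio of arm probabilities under ≥ and under >.

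- SD 1.3, placebo mean 0.3, c = 0.4: 1.290 against 1.293, a shift of about 0.002. Over all SD 1.3 cases the shift is 0.002 to 0.003.
- SD 0.6, placebo mean 0, c = 0.5 (the largest shift found): 2.297 against 2.318, about 0.02.

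These are expected shifts, in which ties in the two arms largely offset each other. In a single trial, one tie in one arm moves the ratio more. With an illustrative 90 and 70 responders, 90/70 = 1.286 becomes 89/70 = 1.271 or 90/69 = 1.304.

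**The case against.** **The sign may be an artefact.** A ≥ that lost its underline in text extraction would read exactly like this. Other comparison signs in the same text look unreliable: SAP 7.2 shows the lower WAZ stratum as < −3 where Protocol 6.2 and SAP 11.5.1 have ≤ −3, and SAP 7.3 shows the recovery endpoint as WAZ > 2 where the rest has > −2. This stands as a reason to check the source PDF first. It does not dispose of the point, because ≥ survives in the same section and > appears there twice.

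**The intended rule is clear from the rest of the documents.** A programmer who follows Table 8 would use ≥ throughout. That is true, and it makes the correction uncontroversial. But 11.5.5.1 is the section that specifies the model.

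**A reader might infer that the risk ratio will certainly use a different count.** The documents do not support that. They establish a different definition. The counts differ only if some infant lies exactly on a cut-off, which is likely but not certain. The 95% figure is for at least one of three thresholds and depends on a change held to 2 decimals.

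**A reader might also add the floating-point problem to that 95%.** The two are alternatives. Rounding creates exact ties and hence the mismatch between signs; without rounding, the signs agree at 0.3 and 0.4 and the ties are misclassified instead. It is also fair to say that how the difference is stored is mainly programming practice. It belongs in the fix because changing the sign alone would leave ties at 0.3 and 0.4 to machine error.

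**Conclusion.** As the text stands, SAP 11.5.5.1 gives two responder definitions for one secondary endpoint, and the one used in the model departs from the endpoint stated in the protocol and elsewhere in the SAP. About one infant in 354 is affected per threshold at SD 1.3, and up to about two at an assumed SD of 0.6. The expected movement in the crude risk ratio runs from the third decimal to about 0.02. The adjusted ratio was not computed.

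It would be going too far to read this as a material bias in the risk ratio or as a threat to the trial's conclusion. The primary and key secondary analyses use continuous change in WAZ and weight and do not depend on these cut-offs. This is a minor consistency correction. The sizes rest on normality, on 354 evaluable infants, and on placebo means and alternative SDs that the documents do not give. The inconsistency itself rests only on the text, subject to the check of the sign in the PDF.

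**What to change.** 1. Check the source PDF of SAP 11.5.5.1. If both model sentences already show ≥, only step 3 remains.
2. Otherwise, write the outcome in both model sentences as: increase in WAZ ≥ 0.3, ≥ 0.4 and ≥ 0.5.
3. Add one sentence: the change in WAZ is rounded to 2 decimals before the thresholds are applied, and a single derived responder flag per threshold is used for the proportions, the models and the listing.

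The cost is two signs and one sentence, made before unblinding. It needs no new data and does not change the protocol endpoint. With one flag, the proportions and the models use the same responder rule.

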6.2 Secondary Objectives

Table 2. Secondary Objectives

Objective		Estimand
Key Secondary		
To evaluate the change in weight of	a)	Population : The mITT population will be used for this analysis.
infants receiving Bi-26	b)	Endpoint : weight change (in grams) from baseline (Day 1) to the Day 56 visit in Bi-26 group.
	c)	Population level summary : Mean change from baseline in weight in the Bi-26 group compared to placebo with stratification blocking factors and feeding regimen covariate(s).
	d)	Intercurrent event(s): Including but not limited to treatment discontinuation.
Secondary		
To estimate the treatment response over time associated with Bi-26	a) b)	Population : The mITT population will be used for the analysis. Endpoint : WAZ change from baseline (Day 1) over time through the Day 90 visit (longitudinal assessment) by duration of dosing.
	c)	Population level summary : Mean change from baseline in WAZ over time in the Bi-26 group compared to placebo with stratification blocking factors and feeding regimen covariate(s).
	d)	Intercurrent event(s): Including but not limited to treatment discontinuation.
To assess the proportion of infants	a)	Population : The Safety population will be used for the analysis.
who achieve a specified change in WAZ from baseline to Day 56	re a specified change in b)	Endpoint : Proportion of infants with $a \ge 0.3$, 0.4, and 0.5 change in WAZ from baseline (Day 1) to Day 56 visit.
	c)	Population level summary : Frequency and percentages of infants with a ≥ 0.3 , 0.4, and 0.5 change in WAZ from baseline (Day 1) to Day 56 in the Bi-26 and placebo groups.
	d)	Intercurrent event(s): Including but not limited to treatment discontinuation.

Confidential Page 11 of 50

To assess the proportion of infants who achieve a specified WAZ at Day 56

- a) **Population**: The Safety population will be used for the analysis.
- b) **Endpoint:** Proportion of infants with a WAZ > -2 at Day 56 visit.
- c) **Population level summary:** Frequency and percentages of infants with a WAZ > -2 at Day 56 in the Bi-26 and the placebo groups.
- d) **Intercurrent event(s)**: Including but not limited to treatment discontinuation.

To assess the re-hospitalization rate

- a) **Population**: The Safety population will be used for the analysis.
- b) **Endpoint:** Number of re-hospitalizations for acute non-surgical illness through the Day 56 visit.

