7.3 Efficacy Measures

The following endpoints will be analyzed for primary efficacy analysis:

• Change in WAZ from baseline to Day 56 visit in the Bi-26 group.

For the secondary endpoints the following will be analyzed:

- Change in weight (in grams) from baseline to Day 56 visit in the Bi-26 group.
- Change in WAZ over time from baseline to Day 90 visit (longitudinal assessment) by duration of dosing.
- Proportion of infants with a $\geq 0.3, \geq 0.4$, and ≥ 0.5 change in WAZ from baseline (Day 1) to Day 56 visit.
- Proportion of infants with WAZ > 2 at Day 56 visit.
- Proportion of re-hospitalizations for acute non-surgical illness through Day 56 visit.
- Presence of *B. infantis* in engraftment stool samples on Days 1, 28, 56, and 90.

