8.1.3 Safety Population

All participants randomly assigned to study intervention, who received any dose, including a partial dose, of the study intervention. Participants will be analyzed according to the intervention they actually received.

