8.1.4 Modified Intention to Treat Population

All participants randomly assigned to study intervention, who received at least one dose (including a partial dose) of the study intervention. Participants will be analyzed according to the intervention they were randomized to.

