8.1.5 Per-Protocol (PP) Population

All participants randomly assigned to study intervention, who received the study intervention, have a Day 90 visit, and did not substantially deviate from the protocol procedures. Important protocol deviations will be evaluated individually by the sponsor to decide whether it has basis to exclude a participant from the PP population. Deviation from study intervention compliance (see Section 11.4) is defined as compliance of less than 80%. Participants will be analyzed according to the intervention they actually received (for details refer to Section 11.1).

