9 CHANGES IN CONDUCT OR PLANNED ANALYSES FROM THE PROTOCOL

- Dynamic randomization will include all stratification variables, including WAZ in determining the treatment allocation.
- Populations for secondary endpoints previously PP, changed to Safety with results to be reported for PP populations as sensitivity analysis.

Confidential Page 21 of 50

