11.5.7.1 Subgroup analysis

The number and proportion with 90% CIs of infants that were re-hospitalized for acute non-surgical illness by Day 56 may be presented in a table by treatment group for subgroups as specified in Section 8.2. The binomial mid-P method will be used to estimate the CIs. Results will be presented for the mITT population.

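### Three secondary efficacy endpoints have no main as-randomised comparison, and the SAP names conflicting populations for longitudinal WAZ (minor; free to fix)

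*SAP*

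**What the plan says.** SAP 7.3 lists one primary and six secondary efficacy measures. For the two WAZ responder endpoints (11.5.5.1 and 11.5.6.1) and for re-hospitalisation (11.5.7), the text is the same: "The Safety and PP populations will be used for this analysis". SAP Table 2 (Section 6.2) gives the estimand population for all three as "The Safety population will be used for the analysis", and Table 8 in Appendix 3 lists Safety and PP.

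The grouping rules differ by population:

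- Safety (8.1.3): "Participants will be analyzed according to the intervention they actually received". PP (8.1.5) follows the same rule and is limited to infants "who received the study intervention, have a Day 90 visit, and did not substantially deviate from the protocol procedures".
- mITT (8.1.4): "Participants will be analyzed according to the intervention they were randomized to". Its membership rule is the same as that of Safety: randomised, with at least one full or partial dose.

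The protocol (9.7, Table 5) had assigned these endpoints to PP. SAP Section 9 declares the change: "Populations for secondary endpoints previously PP, changed to Safety with results to be reported for PP populations as sensitivity analysis". For the optional re-hospitalisation subgroup table, however, 11.5.7.1 says "Results will be presented for the mITT population".

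For WAZ over time, SAP Table 2 names mITT, while the first sentence of 11.5.4.1 takes the Day 90 difference from the model fitted in PP.

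**The concern.** A randomised trial's efficacy comparisons should rest on the groups that randomisation created. Once infants are regrouped by what they received, any error in supply moves them between arms, and the comparison is no longer protected if those errors are related to site, severity or follow-up. PP does not fill the gap. It also groups by product received, and it selects on events after randomisation, including attendance at Day 90 for endpoints that are complete by Day 56.

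The SAP gives no reason for treating these three differently. The two responder endpoints dichotomise the same Day 56 WAZ that the primary analysis uses in mITT. SAP 7.3 lists "Proportion of re-hospitalizations for acute non-surgical illness through Day 56 visit" among the efficacy measures, yet its overall result would follow one grouping rule and its subgroup table another.

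The longitudinal WAZ inconsistency is a smaller matter of the same kind. As written, it is unclear which population gives the main Day 90 result, and one candidate admits only infants who attended Day 90.

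**Working it through.** No sample-size or power figure in the plan bears on this point, so the check is mainly a tabulation.

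**Step 1. Match each measure in SAP 7.3 (1 primary + 6 secondary = 7) to its population.**

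| Measure | Populations named | As-randomised analysis? |
|---|---|---|
| WAZ change to Day 56 (11.5.2) | mITT; PP as sensitivity | Yes |
| Weight change to Day 56 (11.5.3) | mITT; summary table repeated in PP | Yes |
| WAZ over time (Table 2; 11.5.4.1) | mITT and PP, inconsistently | Yes |
| WAZ gain at 0.3, 0.4, 0.5 (11.5.5.1) | Safety, PP | No |
| WAZ above -2 (11.5.6.1) | Safety, PP | No |
| Re-hospitalisation (11.5.7) | Safety, PP | No, apart from optional subgroups |
| *B. infantis* in stool (11.5.8) | mITT, PP | Yes |

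Four have an as-randomised analysis and three do not.

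**Step 2. Look for other mITT output on the three.** There are two items. The re-hospitalisation subgroup table in 11.5.7.1 is optional. The WAZ listing in 11.5.2.1 is an mITT listing and will carry flags for both responder endpoints. Neither provides an overall comparison between arms.

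**Step 3. What changes if mITT replaces Safety.** Membership is identical, so no infant is gained or lost. Only wrongly supplied infants change group. With 198 per arm (SAP 7.1.3), equal numbers of errors in each direction leave 198 v 198. A single infant randomised to Bi-26 but given placebo makes the by-product totals 197 v 199.

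**Step 4. Distance between the two groupings.** The documents give no error rate, so the responder rates and error counts here are assumed. Let k infants in each arm of n receive the other product, with f = k/n, and let p1 and p0 be the rates by product received. As randomised, the Bi-26 rate is p1(1 - f) + p0·f and the placebo rate is p0(1 - f) + p1·f. The difference is therefore (p1 - p0)(1 - 2f).

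- Difference of 10.0 points, n = 198: 10 × (1 - 2k/198) = 9.9 for k = 1, 9.8 for k = 2, 9.6 for k = 4.
- Risk ratios, with n = 177 (the required number per group in SAP 7.1.3):

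| Assumed rates, Bi-26 v placebo | By product received | k = 1 | k = 5 | k = 10 |
|---|---|---|---|---|
| Responder, 50% v 35% | 1.429 | 1.423 | 1.400 | 1.371 |
| Re-hospitalised, 10% v 15% | 0.667 | 0.670 | 0.683 | 0.699 |

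Example, responder with k = 5: f = 5/177 = 0.0282; (0.50 - 0.15 × 0.0282)/(0.35 + 0.15 × 0.0282) = 0.4958/0.3542 = 1.400.

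These figures show only how far apart the two analyses can lie when errors are unrelated to outcome. They show dilution under as-randomised grouping and do not demonstrate bias in the by-product analysis.

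**Step 5. Longitudinal WAZ, the statements side by side.**

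- SAP Table 2: mITT.
- SAP 11.5.4.1, first sentence: PP. Its second sentence adds a compliance-adjusted model in both mITT and PP.
- SAP Section 9: secondary endpoints formerly in PP move to Safety. Protocol Table 5 had this endpoint in PP, so a literal reading gives Safety.
- SAP 11.5.2.4.1 and Table 8: the PP version of the model is a sensitivity analysis.
- SAP 11.5.2.1: the mITT model already yields treatment differences at Days 28, 56 and 90.

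The result that Table 2 calls for is therefore already planned, and only the labels conflict.

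**The case against.** The strongest reply is that the defect may never show. Safety and mITT contain the same infants, and allocation is central through an interactive web system (Protocol 6.2). With no dispensing errors the two analyses are identical. That stands, and it is why the point is minor.

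The move from PP to Safety is openly declared and improves on the protocol, because it restores every dosed infant. That also stands, but it does not restore randomised grouping.

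Re-hospitalisation has a safety side: hospitalisation is a seriousness criterion (Protocol 10.2.2), and the listing in 11.5.7 links each admission to its SAE. This gives Safety some rationale there. But Protocol 8.2 and SAP 7.3 class the endpoint as efficacy, and the SAP's own subgroup table uses mITT. SAE reporting can stay in Safety either way.

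It can also be said that grouping by product received recovers the assumed effect in the illustration, while as-randomised grouping dilutes it. That is true when errors are unrelated to prognosis. The as-randomised comparison does not need that assumption.

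For longitudinal WAZ, 11.5.2.4.1 and Table 8 make the intended role of PP fairly clear. What remains is conflicting text.

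A reader might infer more than the documents support:

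- That the three endpoints appear nowhere in mITT. Responder flags and an optional subgroup table do.
- That any dispensing error makes arm totals differ from the primary analysis. Only unbalanced errors do.
- That the planned results are biased. The documents give no error rate and no evidence of selective errors.

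**Conclusion.** The point holds as a minor one. Three of seven efficacy measures lack a main comparison between randomised groups, although a population with the same infants and the right grouping is already defined and used elsewhere in the SAP. The numerical effect is zero without mis-dispensing and small for a few errors: an assumed 10.0-point difference becomes 9.6 with four swaps in each arm of 198. That size rests on assumed rates, on equal numbers of errors in each direction, and on errors unrelated to outcome. The primary and key secondary endpoints use mITT and are untouched by this grouping issue. The population for longitudinal WAZ is stated inconsistently, but the mITT Day 90 contrast is already planned, so that part is a matter of naming the main result.

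**What to change.** Before unblinding:

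- In SAP Table 2, Section 9, 11.5.5 to 11.5.7 and Table 8, name mITT as the main population for the two WAZ responder endpoints and for re-hospitalisation, with PP as sensitivity. Keep Safety for safety outcomes.
- Reword 11.5.4.1 and Section 9 to agree with Table 2: the mITT Day 90 contrast from 11.5.2.1 is the main longitudinal result, and PP is sensitivity.

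The cost is SAP wording and a population flag in the programs. No new data are needed and the number of infants analysed does not change. The main results for the three endpoints change only if product was mis-dispensed.
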